6.4 Covariates and Subgroups

As this is a small Phase II trial, analysis of covariates may be limited in scope. Mechanistic analyses will focus on temporal changes as well as using mechanistic factors as predictors of clinical response. Age will be considered as a possible covariate as previous studies have shown differential results based on age.

Key subgroup comparisons will include the comparison of the eOIT – Randomized to eOIT – Assigned to determine if the efficacy, safety, or immunogenicity of eOIT differs based on tolerance to baked egg.

6.5 Missing Data

Missing data for primary and secondary endpoints has been described in Section 3.3. At the current time, no other adjustments for missing data are currently planned. If upon analysis, missing data issues are identified

then appropriate methods based on the pattern and frequency of missing data will be applied. All methods and results will be provided to allow for sufficient interpretation of the results.

6.6 Interim Analyses and Data Monitoring

The DSMB will convene to review safety data periodically. Given the relatively small total sample size for the study and the interest in precise treatment-specific endpoint estimates (in addition to the treatment contrast results), no formal efficacy-focused early stopping guidelines or plans are proposed. The DSMB will receive regular reports on accrual, dose escalation success, dose-limiting adverse events, OFC-related adverse events, and other adverse events. The DSMB may request additional analyses.

6.7 Multicenter Studies

Five sites participate in this study and randomization occurs within site. Site effects are not anticipated but demographics and baseline characteristics will be reported by site to assess unanticipated site differences.

6.8 Multiple Comparisons/Multiplicity

A two-sided significance level of 0.05 will be used for primary, secondary, and safety endpoints. For planned mechanistic analyses (e.g., temporal changes, differences between responders and non-responders) a p-value of 0.01 will be used to control for the multiplicity of tests.

7 STUDY PARTICIPANTS

7.1 Participant Disposition

Participant disposition will be described in tables by site and treatment group.

A CONSORT diagram will describe the participant disposition and loss to follow-up through the course of the study.

7.2 **Protocol Deviations**

Participant-specific protocol deviations will be described by individual, treatment group and site. Site specific deviations will be described by site. Listings will include a description of the deviation and any action taken as a result.

8 EFFICACY EVALUATION

8.1 Demographic and Other Baseline Characteristics

Demographics and baseline characteristics will be described by site and treatment group. Demographics include gender, age, and ethnicity. Baseline characteristics include medical history (i.e., asthma, other food allergies, etc.), mechanistic characteristics (i.e., egg IgE, egg SPT, etc.), and baseline SCD for the baked egg and egg white challenges. Continuous variables will be summarized using appropriate measures (means and

standard deviations or medians and interquartile ranges). Categorical variables will be described by frequencies and percentages. If the frequency of an individual category is low, the categories may be collapsed for display or analysis purposes.

8.1.1 Concurrent Illnesses and Medical Conditions

History of allergies, asthma, and atopic dermatitis are collected at baseline and at protocol scheduled followups. These factors will be described at baseline and atopic dermatitis will be described at follow-up timepoints.

8.1.2 Prior and Concurrent Medications

Prior and concurrent medications will be collected by self-report. Medications will be WHO Drug Dictionary coded, and described appropriately.

8.2 Measurements of Treatment Compliance

Missed doses are captured on the dosing symptom logs. Number of expected doses and percentage of doses not administered will be calculated as described in Section 3.3. Participants who withdraw early will also be reported and described.

8.3 Efficacy Analyses

The clinical efficacy endpoints are based on oral food challenge results. Mechanistic efficacy analyses are described in Section 11 below. The primary efficacy endpoint is based on the Year 2 sustained unresponsiveness OFC.

8.3.1 Primary Efficacy Endpoint Analysis

The primary efficacy endpoint is binary. This endpoint is based on passing the Year 2 sustained unresponsiveness OFC followed by a successful open feeding. The proportion of participants passing the Year 2 SU OFC will be compared between the Baked Egg and eOIT – Randomized groups using a two-sided 5% level chi-square test (or Barnard's exact unconditional test as appropriate).

A secondary analysis of the primary endpoint will compare the eOIT-Randomized group to the eOIT-Assigned group using a two-sided 5% level chi-square test (or Barnard's exact unconditional test as appropriate).

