Endpoints and analysis: The primary endpoint of the study will be the development of sustained unresponsiveness to a 7444 mg egg white protein OFC followed by open consumption of a whole egg, 8-10 weeks after discontinuing 2 years of daily Baked Egg or Egg OIT. OFCs will be conducted in a supervised setting and safety parameters will be carefully monitored.

Individuals off therapy for 8-10 weeks, successfully demonstrating consumption of 7444 mg egg white protein OFC without dose-limiting symptoms followed by consuming a whole egg will be considered "successes." All others will be considered "failures" with respect to this endpoint. Among all subjects randomized, the number of subjects on each treatment successfully demonstrating sustained unresponsiveness will be compared to those failing to tolerate this quantity by Chi-square analysis.

Expected outcome/potential limitations: The expected outcome is that 40% of Baked Egg vs. 70% of Egg OIT subjects will tolerate 7444 mg egg white protein OFC, 8-10 weeks after discontinuing Egg OIT or Baked Egg products. The primary limitation to the study is the possibility that we have over-estimated the number of subjects who will tolerate the therapies or subjects do not adhere to dietary restrictions.

Secondary Objectives:

1. Determine the percentage of subjects who can successfully consume without dose limiting symptoms at least 4444 mg egg white protein of a 7444 mg egg white protein OFC after the initial desensitization phase of approximately 1 year of the study and at 2 years.

Rationale: Subjects allergic to egg often have accidental allergic reactions to small amounts of egg in other foods. Generally, the amount of egg causing these accidental allergic reactions is less than 500 mg of egg protein. Previous studies suggest that the continuous administration of a food allergen leads to a "desensitized" state in which an allergic subject will be unresponsive to the ingestion of a food allergen as long as they continue to ingest a small amount of the food on a daily basis.⁸⁰ Food challenges of egg white solid can be done to determine if accidental ingestions of typical amounts of egg could occur without adverse effects.

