Overview of methods: Subjects will undergo the defined therapy programs. At 1 year following 8 weeks on a stable maintenance dose, the subjects will be challenged with a 7444 mg egg white protein OFC. Build up dosing will continue after the 7444 mg egg white protein OFC for subjects who did not reach the maximum daily dose. At 2 years an additional 7444 mg egg white protein OFC will be performed. To date, the investigators have performed more than 10,000 oral food challenges [20% - 25% to egg protein] without a serious life-threatening anaphylactic reaction (the anticipated rate of severe anaphylaxis would therefore be <0.1%).⁷⁹

Endpoints and analysis: Secondary endpoints of this study include the development of a desensitized state as determined from the food challenges while therapy is ongoing. The number of subjects on each treatment tolerating at least 4444 mg egg white protein of a 7444 mg egg white protein OFC will be compared to those who do not by Chi-square analysis.

Expected outcome/potential limitations: It is expected that the majority of subjects will tolerate at least 4444 mg egg white protein of a 7444 mg egg white protein OFC following 40 to 48 weeks of therapy. The primary limitations of the study will be ensuring the safe administration of the daily Baked Egg and Egg OIT dose to all subjects and the possibility that we have over-estimated the number of subjects who will be maintained on maintenance treatment. If an insufficient number of subjects reach maintenance therapy, we may have insufficient power to attain a significant conclusion.

2. Determine the incidence of all serious adverse events.

Rationale: Serious adverse events will serve as a marker of safety for this protocol. As all serious adverse events will be collected for all subjects enrolled in this study, comparison of event rates and types will be made between the treatment arms.

Overview of methods: All serious adverse events will be collected through standard adverse event reporting. This information will be gathered on specific adverse event case report forms and submitted electronically to the Statistical and Clinical Coordinating Center (SACCC). The medical monitor will review each individual report. All serious adverse events will be MedDRA

coded for effective comparison of events. All expedited reports in addition to summary reports will be presented to the DSMB.

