Endpoints and analysis: Serious adverse event rates and types of events will be compared between those receiving Egg OIT and those receiving Baked Egg.

Expected outcome/potential limitations: Comparing serious adverse event rates will serve as a measure of safety in implementing Egg OIT vs. Baked Egg as a therapy for food allergy. This comparison may be limited by the small sample size. It may also be limited if serious adverse events occur rarely. However, if serious adverse events occur rarely in both arms, it would support the safety of the therapy as administered in this protocol and not preclude further clinical investigation.

3. Characterize unrestricted egg consumption after conclusion of treatment via long term followup

Rationale: The durability of sustained unresponsiveness following Egg OIT is currently unknown. Previous studies in other foods have indicated a return to reactivity without continued consumption while results from the prior Egg OIT trial indicate that treatment effect may be durable. Following subjects longitudinally to assess diet and frequency of consumption will aid in understanding the long term impact of Egg OIT.

Overview of methods: Subjects will be contacted annually through September 2018 to complete a phone questionnaire assessing diet and frequency of consumption. Questionnaires will be completed based on time from randomization.

Endpoints and analysis: The endpoint of interest is unrestricted consumption of egg in the diet. Other endpoints including frequency of consumption and any reactions will also be solicited. The analysis will be primarily descriptive with rates of unrestricted consumption described by treatment group and final study status. Numbers permitting, formal comparisons between treatment groups may be performed similar to the primary analysis.

Expected outcome/potential limitations: The number of subjects consenting to be followed longitudinally after two years of treatment may be lower than anticipated. Further, the questionnaire is self-report and likely will be subject to recall bias. As the purpose of this analysis is primarily descriptive these are considered acceptable limitations.

Tertiary Objectives - Mechanistic:

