9.1 Study Endpoint Assessment

9.1.1 Primary Endpoint

The primary endpoint is defined in Section 3.1.1. For the randomized portion of the study an intent-to-treat analysis will be performed. Sustained unresponsiveness can only be demonstrated after discontinuation of active therapy for 8-10 weeks. Individuals successfully demonstrating dose limiting symptom-free consumption of 7444 mg egg white protein by OFC (i.e., dose-limiting symptom-free dosing followed by meal size portion) will be considered successes. All others will be considered to be failures with respect to this endpoint. Analysis will be via the Chi-square test.

9.1.2 Secondary Endpoints

The secondary endpoints are defined in Section 3.1.2.

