4.4.2 Method of Assigning Participants to Treatment Groups (Randomization)

Randomization was performed using an online data system with participants allocated in a 1:1 fashion to eOIT or baked egg consumption stratified by site. The first 40 participants to fail the initial baked egg challenge were assigned to receive eOIT. Further baked egg OFC failures were considered screen failures and not enrolled.

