8.3.2 Secondary Efficacy Endpoint Analyses

Secondary efficacy endpoints include:

1. Desensitization \geq 4444 mg egg white protein at 1 year and 2 year OFC

This endpoint will be described by group via frequencies and proportions and compared between the Baked egg and eOIT – Randomized group using a two-sided 5% level chi-square test (or Barnard's exact unconditional test as appropriate). A secondary comparison will compare the eOIT-Randomized and eOIT-Assigned using a similar method.

2. Unrestricted consumption of unbaked egg at long term follow-up

This endpoint will be assessed on the long term follow-up questionnaire (LFQ). Frequencies and proportions will be described by group and compared between the Baked egg and eOIT – Randomized group using a two-sided 5% level chi-square test (or Barnard's exact unconditional test as appropriate). A secondary comparison will compare the eOIT-Randomized and eOIT-Assigned using a similar method.

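### Randomisation is stratified by site but the randomised efficacy comparisons are not: a valid plan, where a site-stratified test would change power by about -1 to +3 points

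*SAP*

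**What the plan says.** SAP 4.4.2 describes "participants allocated in a 1:1 fashion to eOIT or baked egg consumption stratified by site". SAP 6.7 confirms that there are five sites with randomisation inside each, and adds: "Site effects are not anticipated but demographics and baseline characteristics will be reported by site to assess unanticipated site differences".

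The tests do not use that structure. SAP 8.3.1 compares the two randomised groups on the primary endpoint "using a two-sided 5% level chi-square test", with Barnard's exact unconditional test as the alternative. For desensitization, SAP 8.3.2 says "This endpoint will be described by group via frequencies and proportions and compared between the Baked egg and eOIT" – Randomized by the same test, and it treats long-term consumption of unbaked egg in the same way.

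The Protocol agrees. In section 2.1, successes on the primary endpoint "will be compared to those failing to tolerate this quantity by Chi-square analysis", those reaching the desensitization threshold "will be compared to those who do not by Chi-square analysis", and for long-term follow-up "formal comparisons between treatment groups may be performed similar to the primary analysis". Section 9.1.1 states: "Analysis will be via the Chi-square test".

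Neither document adds a site-stratified test, a site term or a site-adjusted sensitivity analysis for these endpoints. SAP 6.3 limits the efficacy population to participants who start treatment, so exact balance within site can be disturbed after randomisation.

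**The concern.** Stratifying by site makes the arms similar in their site mix. If success rates differ between sites, the observed difference then varies less from trial to trial than the pooled test assumes, because the pooled variance still contains the between-site component. The test becomes conservative and its interval wider than it need be. Analysing by the strata used at randomisation recovers this without new data.

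At stake are a few points of power and some precision, not validity. The choice is worth settling in advance because the trial is open-label: a site-adjusted result introduced after the outcomes were known would carry little weight.

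**Working it through.** **1. The plan's own figure.** Inputs from SAP 5 and Protocol 9.3: 40% vs 70%, two-sided 5%, 96 randomised 1:1, so n = 48 per arm. With a pooled rate of (0.40 + 0.70)/2 = 0.55:

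z = [0.30·√48 − 1.96·√(2·0.55·0.45)] / √(0.40·0.60 + 0.70·0.30) = (2.078 − 1.379)/0.671 = 1.04, so power = 85.1%.

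Exact binomial enumeration of the uncorrected chi-square gives 85.4%. The stated 85% reproduces. With a continuity correction, exact power would be 80.0%, so the plan assumes the uncorrected test.

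**2. The two tests.** With x₁ₖ successes in arm 1 at site k, mₖ successes in both arms there, and Nₖ = n₁ₖ + n₂ₖ:

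- Pooled: (p₁ − p₂)² / [p(1 − p)(1/n₁ + 1/n₂)]
- CMH: [Σ(x₁ₖ − n₁ₖmₖ/Nₖ)]² / Σ[n₁ₖn₂ₖmₖ(Nₖ − mₖ)/(Nₖ²(Nₖ − 1))]

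**3. Why the pooled test becomes conservative.** Take five equal sites with success rates of 13, 23, 38, 55 and 72% (five evenly spaced sites at a log-odds SD of 1.0). Their mean is 40.2%. The pooled variance term is 0.402 × 0.598 = 0.240. The average within-site term is (0.113 + 0.177 + 0.236 + 0.248 + 0.202)/5 = 0.195. The ratio is 0.81. Under balanced allocation and no treatment effect, the pooled test's real critical value is 1.96/√0.81 = 2.18, a true level of about 3%.

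**4. Power under a range of site spreads.** The documents give no spread, so these SDs are assumptions. Site effects are normal on the log-odds scale, the overall rates are held at 40% and 70%, sites are 20/20/20/18/18 with exact balance, and there are 200,000 simulated trials per row (Monte Carlo error about 0.1 point). Size is at 40% in both arms.

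| Site SD | Site rates in the 40% arm | Power, pooled | Power, CMH | Size, pooled | Size, CMH |
|---|---|---|---|---|---|
| 0 | 40% | 85.6% | 85.6% | 5.0% | 4.9% |
| 0.25 | 29–52% | 85.6% | 85.6% | 4.8% | 4.9% |
| 0.5 | 20–63% | 86.1% | 86.8% | 4.5% | 4.9% |
| 0.8 | 12–75% | 86.7% | 88.7% | 3.9% | 4.9% |
| 1.0 | 8–81% | 87.0% | 90.1% | 3.6% | 5.0% |

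The 95% interval half-width, Mantel-Haenszel vs pooled, was 18.3 vs 18.7 points at SD 0.5 and 17.2 vs 18.5 at SD 1.0.

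**5. Imbalance within sites.** With permuted blocks of 4 and 5% not starting treatment (both assumed), CMH minus pooled power was −0.6 points at SD 0, −0.3 at 0.25, 0.0 at 0.35 (site rates 25–57%), +0.6 at 0.5, +2.1 at 0.8 and +3.3 at 1.0. If sites do not differ, CMH costs 0.2 points with blocks of 4 and everyone starting, and 0.6–1.0 when arm counts are off by up to 1–2 per site. With very uneven sites (40/30/14/8/4) and the same imbalance, it costs 0.6–1.2 if small sites are combined and 0.9–1.9 if they are not.

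**6. Versions of CMH that would not help.** With a continuity correction and near-equal sites, CMH power is 80.2% at SD 0. At SD 1.0 with evenly spaced sites it is 86.7%, below the pooled test's 88.9% in the same setting. The exact conditional CMH test has about 80% power at SD 0 and about 82% at SD 0.5. Both are below the pooled test, and the first is below Barnard's 84.9% at 48 per arm.

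**The case against.** The strongest reply is that nothing here falls short of the plan. With 96 analysed, the pooled test holds its size and keeps at least 85% power in every row of the table; the loss exists only relative to another test. SAP 6.7 expects no site effect, and on that premise CMH gains nothing or loses slightly. The 3-point gain needs sites as far apart as roughly 8% and 81% in the same arm. SAP 2.1 and 4.4.2 already describe randomisation in the past tense, so changing a primary test named consistently in both documents has a credibility cost of its own in an open-label trial.

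All of that stands. It limits the point to a minor improvement and makes the change conditional on outcomes not having been tabulated by arm. It does not remove the point: SAP 6.7 itself provides for looking at unanticipated site differences, without saying what would follow for the efficacy test.

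A reader might also infer two further gaps.

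- **Outcome by site.** It cannot be said that success by site will go unreported. The table list is a separate document (SAP 16), and only the SAP text is silent.
- **Age.** SAP 6.4 names age as a possible covariate and SAP 8.3.3 plans exploratory age analyses. One prespecified age-adjusted comparison would be an optional extra and is no part of this point.

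**Conclusion.** The mismatch is real and its consequence is small. The unstratified test is valid and delivers the stated 85% power. Using a site-stratified CMH test instead would change power by between about −1 point, when sites do not differ and allocation is somewhat uneven within sites, and about +3 points at a between-site log-odds SD of 1.0. With some imbalance, break-even is at an SD of about 0.35. Spreads of 1.5 to 2 would give 4 to 6 points, but nothing in the documents suggests them.

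A reader might infer that ignoring the stratification factor invalidates the test or leaves the trial underpowered. Neither follows: the pooled test's error rate falls below 5% as sites diverge, and its power does not fall below plan.

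Site spread, site sizes, block size and the proportion not starting treatment are all assumed. The point concerns only Baked Egg vs eOIT-Randomized. The comparison with eOIT-Assigned is not randomised and is unaffected.

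**What to change.** Minor priority. Before outcomes are tabulated by arm, amend SAP 8.3.1 and 8.3.2 for the randomised contrast only:

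- Compare proportions with the asymptotic CMH test stratified by site, two-sided 5%, without continuity correction.
- Report the Mantel-Haenszel risk difference with its 95% CI.
- Combine any site with fewer than 8 participants in the efficacy population, or none in one arm, with the next smallest site.
- Keep the pooled chi-square or Barnard test as a sensitivity analysis.
- Where an exact test is needed, keep Barnard's test and do not substitute the exact conditional CMH.

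Align the chi-square wording in Protocol 2.1 (primary and desensitization) and 9.1.1. The long-term comparison in Protocol 2.1 is tied to the primary analysis and follows. Record the change in SAP 14. If outcomes by arm have already been tabulated, leave the pooled test as primary and add CMH as supportive only.

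The cost is a dated SAP amendment, a matching Protocol edit and a few lines of code, with no new data or participants. The statistical downside is up to about 1 power point if sites do not differ.

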8.3.2 Secondary Efficacy Endpoint Analyses

Secondary efficacy endpoints include:

1. Desensitization \geq 4444 mg egg white protein at 1 year and 2 year OFC

This endpoint will be described by group via frequencies and proportions and compared between the Baked egg and eOIT – Randomized group using a two-sided 5% level chi-square test (or Barnard's exact unconditional test as appropriate). A secondary comparison will compare the eOIT-Randomized and eOIT-Assigned using a similar method.

2. Unrestricted consumption of unbaked egg at long term follow-up

This endpoint will be assessed on the long term follow-up questionnaire (LFQ). Frequencies and proportions will be described by group and compared between the Baked egg and eOIT – Randomized group using a two-sided 5% level chi-square test (or Barnard's exact unconditional test as appropriate). A secondary comparison will compare the eOIT-Randomized and eOIT-Assigned using a similar method.

8.3.3 Exploratory Efficacy Analyses

Although not specified in the protocol, changes in SCD from baseline to each protocol OFC are of scientific interest. The change in SCD will be compared between treatment using the Wilcoxon Rank Sum test to do pairwise comparisons between treatment groups. Effects of age will also be explored.

Analyses will also consider participants who successfully passed the desensitization OFCs to 7444 mg of egg white protein at the Week 52 and Year 2 OFCs. Comparisons between groups will be assessed in a similar fashion to the secondary endpoints above.

Clinical and immunological predictors of sustained unresponsiveness are of great scientific and medical interest. Of particular interest is the effect of age on treated effect and clinical outcomes. Logistic regression may be used to identify predictors of clinical response (i.e., desensitization and/or sustained unresponsiveness). Predictors will be incorporated into models adjusting for treatment where possible. Transformations will be implemented as appropriate and model fit will be assessed using the Hosmer-Lemeshow goodness of fit test. Area under the curve (AUC) may be used as an assessment of predictor strength. If the number of successes permits, multivariable models may be fit and stepwise regression techniques applied to identify important predictors or combinations of predictors.

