5 SAMPLE SIZE CONSIDERATIONS

The sample size target for the randomized portion of the study is 96 individuals with 1:1 random assignment to Baked Egg and Egg OIT. The sample size was selected to determine whether a difference exists between the treatment groups in the primary endpoint rate for the sustained unresponsiveness-focused portion of the study. Specifically, the sample was designed to have 85% power to detect with a two-sided 5% level test, a difference between a 40% and 70% sustained unresponsiveness rate. While a small dropout rate may occur, we will use all randomized cases who initiate treatment in the intent-to-treat analysis of the primary endpoint; failures associated with noncompliance are include in the denominator for event rates above. This sample size is sufficient to address the secondary endpoint of the desensitization components of the study for event rate differences of comparable size.

The subset of individuals who are not baked egg tolerant at baseline comprise a selected group of individuals where Egg OIT will be examined. The size of the group will be capped at approximately 40 subjects. The study cohort should be useful for both clinical and mechanistic study with approximately 40 such individuals enrolled. The 2 year sustained unresponsiveness rate will be compared to historical experience as well as the protocol's randomized Egg OIT arm. Mechanistic studies will be examined to determine if baseline immune system responses are similar in both Egg OIT groups. Immune parameter

changes will be examined to determine if tolerant and non-tolerant cases have response profiles that are parallel for the 2 strata.

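### SAP 8.3.3 plans no validation or optimism correction, so an AUC reported after selecting predictors in the same children can be biased upward

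*SAP*

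**What the plan says.** SAP 8.3.3 is headed as exploratory. Logistic regression may be used to find predictors of desensitization and/or SU, and "Predictors will be incorporated into models adjusting for treatment where possible". Fit is to be checked by the Hosmer-Lemeshow test. On performance, the section says "Area under the curve (AUC) may be used as an assessment of predictor strength". The next sentence says that, provided there are enough successes, "multivariable models may be fit and stepwise regression techniques applied to identify important predictors or combinations of predictors".

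The section gives no candidate list, time points, entry or stay level, or number of successes that would suffice. Neither document mentions a split sample, cross-validation, bootstrap or any other correction of the AUC.

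The only related threshold is 0.01. SAP 6.8 sets it for planned mechanistic analyses, and Protocol 9.5 for clinical associations with mechanistic outcomes. Neither place calls it the entry level for stepwise selection.

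**The concern.** An AUC computed in the children who were used to choose and fit a model overstates how well that model will do in other children. The overstatement grows with the number of markers searched and shrinks with the number of children. Here the pool of markers is large and the trial is small.

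The SAP describes predictors of SU as scientifically and medically important, and Protocol 1.2 and 2.1 look to biomarkers for predicting the course of egg allergy. A published AUC from this section could therefore be taken as evidence of predictive value. What is at stake is the credibility of an exploratory biomarker result. The treatment comparison is not at stake.

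**Working it through.** **The plan's own figure.** SAP 5 claims "85% power to detect with a two-sided 5% level test, a difference between a 40% and 70% sustained unresponsiveness rate" with 96 children randomized 1:1. With a pooled rate of 0.55 and no continuity correction:

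n per arm = [1.960 × √(2 × 0.55 × 0.45) + 1.036 × √(0.40 × 0.60 + 0.70 × 0.30)]² / 0.30² = (1.379 + 0.695)² / 0.09 ≈ 47.8, so 48 per arm and 96 in all. Power at 48 per arm is 85.1%. The figure reproduces. The SAP gives no figure for the predictor analysis.

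**Inputs from the documents**
- Children: 96 randomized (SAP 5). The efficacy population in SAP 6.3 also includes the eOIT-Assigned group of about 40, so 96 + 40 = 136 is possible. Mechanistic analyses use only children with samples, so the number could also be smaller.
- SU rate: 48 × 0.40 + 48 × 0.70 = 52.8 successes, or 55%. As a lower value, 27.5% from the earlier egg OIT trial (Protocol 1.1).

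**Inputs that are assumptions**
- Candidates: none are listed. A count of the variables derived in SAP 3.3, at one time point and without the delta versions, gives 14 (seven 6-hour markers, count and percentage) + 10 (five 18-hour markers, count and percentage) + 3 total cell counts + 1 Th2:Treg ratio + 2 IgE/IgG4 ratios + 1 basophil measure = 31. Adding egg IgE, IgG4, total IgE, skin test, age and two baseline consumed doses gives 38. The range used is 10, 20 and 40.
- Entry level: 0.01, 0.05 and 0.15.
- Markers: independent, standard normal, unrelated to outcome.

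**Method.** Each setting had 400 simulated trials. Stepwise logistic regression used score-test entry and Wald removal at the same level. Apparent AUC came from the fitting sample and was set to 0.50 if no term was in the model. The same model was then applied to 4,000 new subjects. With 400 runs, the standard error of a proportion is at most √(0.25/400) = 0.025.

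**Pure noise, treatment not in the model.** Entries are mean apparent AUC and, in brackets, the share of runs with AUC of 0.70 or more. AUC in new subjects is 0.50 throughout.

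| N | SU rate | Entry | 10 candidates | 20 | 40 |
|---|---|---|---|---|---|
| 96 | 55% | 0.01 | 0.51 (0.3%) | 0.53 (3%) | 0.55 (8%) |
| 96 | 55% | 0.05 | 0.55 (6%) | 0.60 (15%) | 0.68 (46%) |
| 96 | 55% | 0.15 | 0.61 (10%) | 0.69 (47%) | 0.80 (92%) |
| 96 | 27.5% | 0.05 | 0.56 (8%) | 0.61 (21%) | 0.70 (54%) |
| 136 | 50% | 0.05 | 0.55 (1%) | 0.59 (7%) | 0.65 (22%) |

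Repeat runs at N = 96, 55% and entry 0.05 gave 0.61 (20 candidates) and 0.67 (40).

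**How often noise is selected (N = 96, 55%).** At entry 0.05, 34%, 62% and 85% of runs with 10, 20 and 40 candidates select something. At 0.01 the figures are 4%, 15% and 26%. The simple bound for 40 candidates at 0.01 is 1 − 0.99⁴⁰ = 33%, so a quarter to a third is a fair range.

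**AUC when something is selected (entry 0.01, 40 candidates).** The overall mean of 0.549 mixes 74% of runs at 0.50 with 26% above it: (0.549 − 0.74 × 0.50) / 0.26 = 0.69.

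**Best single marker, no stepwise.** Picking the best of 40 noise markers at N = 96 gives a mean AUC of 0.64 (SU 55%) to 0.66 (SU 27.5%).

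**Treatment in the model at 40% and 70%.** The Egg OIT share of successes is 0.70/1.10 = 0.636, and of failures 0.30/0.90 = 0.333. The AUC of treatment alone is 0.5 + (0.636 − 0.333)/2 = 0.65. After stepwise addition of noise (N = 96):

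| Entry | Candidates | Apparent AUC | AUC in new subjects |
|---|---|---|---|
| 0.05 | 20 | 0.71 | 0.63 |
| 0.05 | 40 | 0.76 | 0.61 |
| 0.01 | 40 | 0.68 | 0.64 |

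At entry 0.05 the selected model looks better than treatment alone and predicts slightly worse.

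**The case against.** The strongest reply is that the SAP commits to very little. Every step is optional, stepwise selection waits on the number of successes, and the AUC sentence comes before the stepwise sentence without being tied to it. A reader might infer that predictors will be chosen stepwise and then judged by AUC in the 96 randomized children. The text does not say that. This part of the reply stands. It does not remove the point, because choosing the best single marker by AUC inflates the value as well.

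Second, 0.01 is the documents' only threshold for mechanistic associations. At that level most noise runs select nothing and the mean AUC stays near 0.55 even with 40 candidates. This also stands in part. However, 0.01 governs significance tests, is not stated as the entry level, and does not correct an AUC. When a noise marker does get through, the apparent AUC averages about 0.69.

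Third, many variables in SAP 3.3 are counts, percentages and deltas of the same cells. They will be correlated, so 40 independent candidates probably overstates the search. That is fair, and the inflation would be smaller than simulated.

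Fourth, the section is exploratory, SAP 6.4 expects covariate work to be limited, and age is the one predictor singled out. That limits the importance of the point but does not make an uncorrected AUC unbiased.

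**Conclusion.** The point holds as a minor one. SAP 8.3.3 permits selection among many markers and permits AUC as the measure of strength, with no correction planned, so any AUC reported in the same children after selection can be too high.

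At entry 0.05 with 96 children, the mean excess on pure noise is about 0.10 with 20 candidates and 0.17 to 0.18 with 40. With 136 children and 40 candidates it is about 0.15. With treatment in the model, the gap between apparent AUC and AUC in new subjects is about 0.08 (20 candidates) and 0.15 (40). These sizes rest on an assumed number of independent candidates, entry level and sample size, none of which the SAP fixes for this analysis.

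A reader might go further and conclude that the trial will report a useful-looking predictor from noise. The documents do not support that: with 10 candidates at 0.05, or at 0.01, most noise runs select nothing. The primary and secondary tests and the sample size are untouched.

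**What to change.** State in SAP 8.3.3 that any AUC reported after variable selection, whether stepwise or by choosing the best single marker, will be optimism-corrected by repeating the whole selection within bootstrap samples or cross-validation. Report the corrected value beside the AUC of treatment alone, so that the reader sees what the markers add. Listing the candidates, time points and entry level in the same place would let the size of the search be judged.

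The cost is a few sentences, some computing and less favourable AUCs. No new data are needed, and SAP 14 already provides for updates.
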